6.1.3 Treatment arms/group

Subjects will be assigned to one of the following 2 treatment groups in a randomization ratio of 2:1, for a total of 8 weeks:

- Group 1: LYS006 20 mg BID
- Group 2: matching placebo BID

Subjects will take 4 capsules of 5 mg at each dose to make up to 20 mg. There will be a morning and evening dose (4 capsules each) for all subjects.

All subjects will receive their respective supply of LYS006 or placebo capsules every 4 weeks during their scheduled visits to the site.

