12.1 Analysis sets

For all analysis sets, subjects will be analyzed according to the study treatment(s) received.

The safety analysis set will include all subjects that received any study drug.

Commercially Confidential Information

The PD analysis set will include all subjects who received any study drug and had no protocol deviations with relevant impact on PD data.

Commercially Confidential Information

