12.4 Analysis of the primary endpoint(s)

The primary aim of the study is to assess the induction of clinical remission by LYS006 compared to placebo in patients with mild to moderate ulcerative colitis. The PD analysis set will be used for the primary analysis.

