12.4.1 Definition of primary endpoint: Clinical remission

The primary endpoint of this study is the clinical remission rate at the End of treatment (EoT) visit (CCI Week 8 for subsequent protocol amendments), i.e. the proportion of the patients who reach the status of clinical remission at the EoT visit.

Clinical remission is defined as a full Mayo score of 2 points or lower, with no individual subscore exceeding one point.

Subjects with early discontinuation for reasons other than COVID-19 before the EoT visit, or use of rescue/prohibited medication during the treatment period, or missing endoscopy score at EoT will be considered failed to reach remission.

Discontinuation prior to the defined treatment period, or subjects who were not able to complete endoscopy at EoT visit due to local COVID-19 related restrictions will be considered as missing data.

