## 4 Statistical methods: Analysis sets

For all analysis sets, subjects will be analyzed according to the study treatment(s) received.

The safety analysis set will include all subjects that received any study drug.

Commercially Confidential Information

The PD analysis set will include all subjects who received any study drug and had no protocol deviations with relevant impact on PD data.

The data collected from the subjects      Commercially Confidential Information

Commercially Confidential Information

will be pooled for all the analyses listed in this document.

The analysis sets and protocol deviation codes are related as follows:

**Table 4.1** Protocol deviation codes and analysis sets

Category Deviation code	Text description of deviation	Data exclusion
	Subjects are excluded from all (safety) analysis in case of these protocol deviations:	Exclude subject completely from all (safety) analysis sets
INCL01	Deviation from inclusion criterion 1 (Written informed consent must be obtained before any assessment is performed)	Yes

Category Deviation code	Text description of deviation	Data exclusion
Commercially Confidential Information		
Subjects are excluded from PD analysis in case of these protocol deviations:		
INCL01	Deviation from inclusion criterion 1 (Written informed consent must be obtained before any assessment is performed)	Yes
TRT04	Wrong dose of study drug	Yes
OTH12PA2	Change in Standard of Care treatment	Yes

Commercially Confidential Information

---

If updates to this table are needed, an amendment to the SAP needs to be implemented prior to DB lock.

Commercially Confidential Information

Commercially Confidential Information

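### As far as the visible text shows, SAP Table 4.1 drops every subject coded as wrong dose from the primary remission analysis, which cuts across the failure rules and can move the decision either way

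*SAP*

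**What the plan says.** Protocol 12.4 names the analysis population: "The PD analysis set will be used for the primary analysis". Both documents define that set in general terms. Protocol 12.1 admits treated subjects who "had no protocol deviations with relevant impact on PD data", and SAP section 4 repeats the definition.

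SAP Table 4.1 makes the general phrase operational. Under the heading "Subjects are excluded from PD analysis in case of these protocol deviations" it lists TRT04, "Wrong dose of study drug", with a plain Yes in the exclusion column. The visible row gives no number of doses, amount, duration or timing. Parts of the table and the text around it are redacted.

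Other events after randomisation are treated differently. Under protocol 12.4.1, "Subjects with early discontinuation for reasons other than COVID-19 before the EoT visit" count as not having reached remission, and so do users of rescue or prohibited medication and those with no endoscopy score at end of treatment (EoT). All of them stay in the denominator. Protocol 12.4.3 and SAP 6.1.3.1 follow the same approach and extend it to any missing subscore, apart from COVID-19 cases, which are treated as missing.

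On dosing, protocol 6.1.3 states: "There will be a morning and evening dose (4 capsules each) for all subjects". Most doses are taken at home over 8 weeks. SAP 7.2 lists dose changes and missed doses, but says that capsule accountability is not in the CRF, so compliance will not be analysed.

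**The concern.** Exclusion for a wrong dose is decided by something that happens after randomisation and may be related to how the subject is doing, for example if capsules are cut because of an adverse event or worsening. Where that link exists and differs between arms, removing those subjects distorts the comparison that randomisation was meant to protect.

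The rule also works against the plan's own logic. Elsewhere the plan guards against this distortion by counting post-randomisation events as failures. TRT04 instead removes the subject from numerator and denominator. For a subject with a wrong dose who later stops early or receives rescue, 12.4.1 gives failure and Table 4.1 gives no record. No visible sentence says which prevails.

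The decision rests on about 45 subjects, with no replacement planned (protocol section 5), so a few subjects carry weight. The visible text contains no primary analysis in all treated or all randomised subjects that would show the effect of the exclusions.

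**Working it through.** **Inputs.** Arm sizes are 30 and 15 (protocol 12.8.1). The LYS006 prior is Beta(1/3, 1/3). The placebo prior is 0.43 Beta(18.9, 167.4) + 0.34 Beta(3.2, 24.2) + 0.03 Beta(1.0, 3.3) + 0.2 Beta(1, 1) (protocol 12.4.2, SAP 6.1.3). A go means that both dual criteria are met: Prob(diff > 0) > 90% and Prob(diff > 15%) > 50%.

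**Formulas.** With x remitters of n on LYS006 and y of m on placebo:
- LYS006 posterior: Beta(1/3 + x, 1/3 + n − x).
- Placebo posterior: a mixture of Beta(a_k + y, b_k + m − y), with weights proportional to w_k · B(a_k + y, b_k + m − y) / B(a_k, b_k).
- Prob(diff > d) = ∫ f_placebo(p) · Prob(LYS006 rate > p + d) dp, by numerical integration.

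**Assumptions.** The placebo rate in 12.8.1 is redacted; I use 11.5%. The SAP's baseline Mayo covariate is not modelled.

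**The plan's own figures.** At a true 25-point difference the chance of a go is 85.0%, 86.0%, 86.3% and 86.6% for placebo rates of 10%, 11%, 11.5% and 12% (stated: 86%). With no difference and 11.5% in both arms, the chance of a go is 1.9% (stated: below 5%) and of meeting neither criterion 92.5% (stated: 92%). The model is therefore close enough to use. The match is partly a fit, because the placebo rate had to be chosen.

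**Effect of single exclusions near the boundary.**

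| LYS006 | Placebo | Prob(diff > 0) | Prob(diff > 15%) | Result |
|---|---|---|---|---|
| 7/30 | 1/15 | 96.1% | 43.2% | no-go |
| 7/28 (two non-remitters removed) | 1/15 | 97.0% | 50.9% | go |
| 10/30 | 4/15 | 89.2% | 55.8% | no-go |
| 10/29 (one non-remitter removed) | 4/15 | 90.2% | 59.3% | go |
| 8/30 | 1/15 | 98.1% | 58.6% | go |
| 7/29 (one remitter removed) | 1/15 | 96.6% | 47.0% | no-go |
| 8/30 | 2/15 | 96.0% | 51.8% | go |
| 8/30 | 2/13 (two placebo non-remitters removed) | 94.7% | 49.7% | no-go |

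**Effect on the chance of a go.** Removal fractions of 10% and 20% are assumed; the documents give none.

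| Who is removed | No true difference: 0 / 10% / 20% | True 10-point difference: 0 / 10% / 20% |
|---|---|---|
| LYS006 non-remitters only | 1.9 / 3.1 / 5.7% | 29 / 36 / 45% |
| Subjects regardless of outcome | 1.9 / 2.0 / 2.5% | 29 / 27 / 28% |

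If non-remitters are removed at the same rate in both arms, the false-go chance is about 3% at 10% removal and just under 5% at 20%.

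**The case against.** The strongest reply is that Table 4.1 sits under a definition limited to deviations that matter for PD data, and that protocol 11.2 has relevant deviations determined before lock and unblinding for analysis. On that view TRT04 would be assigned only to serious dosing errors. The trial is also a non-confirmatory proof of concept, where an adherence-based primary set is defensible. Finally, set membership decides who is analysed and 12.4.1 decides response among them, so the two can be applied in sequence.

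Much of this stands as a limit on the point:
- A reader might infer that one miscounted capsule removes a subject, and so that many would be lost. The documents do not support that. No coding criterion for TRT04 is visible, no dosing-error rate is given, and nothing says that each entry in the dosing record becomes a TRT04 deviation.
- A reader might infer that the rule favours LYS006. It applies to both arms and all outcomes. The upward shift needs exclusions tied to non-remission, mainly on LYS006, and the reverse flip is as easy to construct.

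What remains is the rule as written. Once a subject carries the code, the visible table leaves no judgement about relevance. Applying membership first makes the two rules executable, but its result is that a protocol-defined failure vanishes from the denominator. Determining deviations before unblinding limits selective coding, but does not break a link between dosing errors and outcome.

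**Conclusion.** The point holds on the visible text. TRT04 is an unqualified post-randomisation exclusion from the primary set, and it is inconsistent with the way the plan treats discontinuation, rescue and missing endoscopy. Near the boundary, one or two such exclusions decide the result, in either direction.

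The long-run effect is conditional. The false-go chance passes the plan's 5% only in the scenario where 20% of LYS006 non-remitters, and no one else, are removed. It is 3.1% at 10%, and hardly moves when removal is unrelated to outcome. These figures rest on an assumed 11.5% placebo rate and on a model without the baseline Mayo covariate. The number of TRT04 events to expect is not stated, so the actual size cannot be fixed from the documents. A threshold in redacted text would narrow the exclusion, but the order of precedence with 12.4.1 would still need stating.

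The sentence "For all analysis sets, subjects will be analyzed according to the study treatment(s) received" might be read as part of the same fault. It is a separate matter: protocol 12.1 says the same, so analysis by randomised arm would need a protocol change.

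**What to change.** Before database lock, amend SAP Table 4.1 so that TRT04 is no longer a reason for exclusion from the primary remission analysis. State the order of rules: apply the 12.4.1 failure rules first, then use observed EoT remission status for the remaining wrong-dose subjects. Keep TRT04 exclusion as a sensitivity analysis, with a size or duration threshold fixed in advance and based on the dosing data that are collected, since capsule accountability is not. If a threshold already exists in redacted text, cite it there.

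The cost is a SAP amendment, which the note under Table 4.1 already provides for, and one extra run. The downside is slight dilution of the estimated effect by subjects who were truly mis-dosed; the sensitivity analysis would show how much.

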12.4.3 Handling of missing values/censoring/discontinuations

In the primary analysis, subjects who discontinue from the study for reasons other than COVID-19 prior to EoT visit, or have received rescue or prohibited medication for the treatment of ulcerative colitis during the treatment period will be considered failed to reach clinical remission. Discontinuation prior to the defined treatment period, or subjects who were not able to complete endoscopy at EoT visit due to local COVID-19 related restrictions will be CCI considered as missing data. Any missing subscore at Week 8 (subsequent protocol amendments) will lead to a non-evaluable clinical remission status and the subject will also be considered failed to reach clinical remission. Reasons for missing Mayo scores or subscores need to be collected to understand the impact of such analysis approach. Imputation methods such as tipping point analysis may be explored.

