## **6 Statistical methods for Pharmacodynamic (PD) parameters**

All subjects within the PD analysis set will be included in the PD data analysis.

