### 6.1.3.1 Model checking procedures

Subjects who discontinued from the study for reasons other than COVID-19 before the EoT visit, or have received rescue or prohibited medication for the treatment of UC during the treatment period will be considered failed to achieve clinical remission. Any CCI data for a subject that were recorded at or after the start of a rescue or prohibited medication should be removed from the CCI statistical analyses.

Any missing subscore will lead to a non-evaluable clinical remission status and the subject will also be considered failed to achieve clinical remission. Reasons for missing Mayo scores or subscores need to be collected to understand the impact of such analysis approach. Imputation methods such as tipping point analysis may be explored.

Discontinuation prior to EoT, or subjects for which central reading of EoT endoscopy was not available due to local COVID-19 related restrictions will be considered as missing data.

Commercially Confidential Information

The homogeneity of the total Mayo scores between subjects  
visually by each visit.

CCI  
will be explored

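### SAP Table 4.1 removes subjects with a standard-of-care change from the primary analysis set, although some of them are also to be counted as non-remitters, and no visible text says which rule governs

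*SAP*

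**What the plan says.** **Analysis set.** Protocol 12.4 assigns the primary analysis to the PD analysis set, and SAP section 6 states: "All subjects within the PD analysis set will be included in the PD data analysis". SAP section 4 admits dosed subjects without a protocol deviation that matters for PD data. Table 4.1 then lists codes under the line "Subjects are excluded from PD analysis in case of these protocol deviations". One of them is OTH12PA2, "Change in Standard of Care treatment", marked Yes for exclusion. The visible row has no qualifier for drug, direction or reason.

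**Endpoint.** Protocol 12.4.1 names "use of rescue/prohibited medication during the treatment period" among the reasons for scoring a subject as not in remission. Protocol 12.4.3 repeats this for the primary analysis: subjects who "have received rescue or prohibited medication for the treatment of ulcerative colitis during the treatment period will be considered failed to reach clinical remission". SAP 6.1.3.1 has the same rule: subjects who "have received rescue or prohibited medication for the treatment of UC during the treatment period will be considered failed to achieve clinical remission". For certain analyses, whose names are redacted, SAP 6.1.3.1 adds that data "recorded at or after the start of a rescue or prohibited medication should be removed".

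**Standard of care.** Protocol 6.2.1.1 defines it as 5-ASA plus, where relevant, oral corticosteroids or budesonide, held stable through the treatment period. Inclusion criterion 6 admits patients on such steroids, and Protocol 12.2 summarises their use at baseline. Protocol 6.2.3 gives a raised corticosteroid dose as an example of rescue. Table 6-2 lists steroid doses above set limits as prohibited.

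**The concern.** A subject on a background steroid whose dose is raised as rescue, or goes above the Table 6-2 limits, fits two instructions that give different primary data. SAP 6.1.3.1 keeps the subject in the denominator as a failure. Table 4.1 takes the subject out of numerator and denominator alike. Nothing visible ranks the two.

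If Table 4.1 is followed literally, the exclusion rests on an event that occurs after randomisation and is related to the outcome. Each such exclusion raises the observed remission rate in its arm: on LYS006 it favours the drug, and on placebo it works against it. With about 30 and 15 patients, one or two subjects are a visible share of an arm. If the question is still open when deviations are classified, the choice of denominator becomes a judgement made late in the trial and not a pre-specified rule.

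**Working it through.** **Inputs**
- Sample size (Protocol 12.8): 45 subjects at 2:1, so 30 v 15.
- Priors (Protocol 12.4.2, SAP 6.1.3): LYS006 Beta(1/3, 1/3). Placebo is a mixture of Beta(18.9, 167.4), Beta(3.2, 24.2), Beta(1.0, 3.3) and Beta(1, 1), with weights 0.43, 0.34, 0.03 and 0.2.
- Success: P(diff>0) > 90% and P(diff>15%) > 50%.
- Placebo remission rate: redacted in Protocol 12.8.1. I assume 11.5%. The mean of the three informative components is close to this: (0.43 × 18.9/186.3 + 0.34 × 3.2/27.4 + 0.03 × 1.0/4.3) / 0.80 = 0.0903/0.80 = 11.3%.

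**Method.** With x remitters of n on LYS006, the posterior is Beta(1/3 + x, 1/3 + n − x). With y of m on placebo, each component becomes Beta(a + y, b + m − y), and its weight is multiplied by B(a + y, b + m − y)/B(a, b) and renormalised. P(diff > d) is the integral over the placebo posterior of the probability that the LYS006 rate exceeds the placebo rate plus d, evaluated on a 4000-cell grid. Operating characteristics sum binomial probabilities over all (x, y). This is the unadjusted protocol analysis; the SAP model also includes baseline Mayo score.

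**Step 1: reproduce the plan's figures.** At 36.5% v 11.5%, the chance of meeting both criteria is 86.3% (stated 86%). At 11.5% in both arms it is 1.9% (stated below 5%), and the chance of meeting neither criterion is 92.5% (stated 92%). The smallest LYS006 counts that succeed are 7, 8, 8, 9 and 11 of 30 for 0, 1, 2, 3 and 4 placebo remitters of 15.

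**Step 2: two failures dropped at the boundary**

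| Data | P(diff>0) | P(diff>15%) | Both criteria |
|---|---|---|---|
| 7/30 v 1/15 (all counted) | 0.961 | 0.432 | not met |
| 7/28 v 1/15 (two LYS006 failures dropped) | 0.970 | 0.509 | met |
| 8/30 v 2/15 (all counted) | 0.960 | 0.518 | met |
| 8/30 v 2/13 (two placebo failures dropped) | 0.947 | 0.497 | not met |

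**Step 3: how often a trial ends where such exclusions reverse the decision.** The placebo rate is 11.5%. These figures are conditional on the exclusions occurring.

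| Failures dropped | Reversal | True difference 0 | 15 points | 25 points |
|---|---|---|---|---|
| 2 LYS006 | not met → met | 1.2% | 8.2% | 4.0% |
| 2 placebo | met → not met | 0.9% | 7.9% | 5.3% |
| 2 LYS006 and 1 placebo | not met → met | 1.0% | 4.9% | 1.6% |

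A single exclusion reverses the decision in at most about 1.1% of trials. Over assumed placebo rates of 5%, 11.5% and 20% and true differences of 0 to 25 points, the two-exclusion figures run from under 0.1% to 8.5% (LYS006) and from under 0.1% to 9.9% (placebo).

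**Step 4: average effect.** Here a stated share of each whole arm is excluded, all of them non-remitters, with overall remission held fixed.

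| Share of each arm excluded | Both criteria met, 11.5% v 11.5% | Both criteria met, 36.5% v 11.5% |
|---|---|---|
| 0% | 1.9% | 86.3% |
| 3% | 2.1% | 87.2% |
| 5% | 2.3% | 87.9% |

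With no true difference the figure is 4.2% at 15% excluded and 5.7% at 20%. It passes the stated 5% only at about 20%, a rate that no document supports.

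**The case against.** The best counter-reading is that Table 4.1 concerns protocol deviations, whereas Protocol 6.2.3 expressly allows rescue provided study treatment is stopped. A steroid increase given as rescue would then not be a deviation and would not be coded OTH12PA2. Only the non-remission rule would apply, and the passages would agree. In addition, the code is undefined in the visible text and redacted blocks lie next to it, so a definition or an order of precedence may exist there. On size, the reversal figures presuppose exclusions that may never occur, exclusions spread 2:1 reverse fewer decisions, and the average effect is slight. The study is described as non-confirmatory, and SAP 7.2 lists all deviations, so affected subjects could be identified.

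Much of this stands as a limit. The overlap may be narrow, and redacted text may already settle it. It does not dispose of the point, for two reasons. The reading that rescue is not a deviation is nowhere written in the visible text, and an equally natural one, applying set membership before the endpoint rule, gives the opposite analysis. It also does not cover a background steroid taken above the Table 6-2 limits outside rescue: that breaks the stable-dose requirement and is scored as failure. Listing the deviations identifies these subjects but does not say whether they belong in the primary denominator.

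**Conclusion.** The concern holds on the visible text and should be fixed; confidence is medium. SAP 6.1.3.1 suggests that these subjects were meant to stay in: it gives them an outcome and, for certain analyses, removes only data from the start of the rescue or prohibited medication onwards. Table 4.1, read literally, takes them out.

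The stake is an unsettled primary denominator in a small trial, not a large average bias. Two exclusions in one arm can turn the decision either way near the boundary; away from it the effect is small. The figures rest on the assumed 11.5% placebo rate, the unadjusted model and illustrative exclusion numbers, since the documents give none. The finding is confined to subjects on background steroids. Rescue with a new immunomodulator, other discontinuations and missing scores are outside it.

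**What to change.** Reconcile SAP section 4 with SAP 6.1.3.1 and Protocol 12.4.3 by adding one sentence to section 4, for example: *OTH12PA2 does not remove a subject from the primary endpoint analysis when the change is rescue or prohibited UC medication during the treatment period; the subject stays in the PD set as a non-remitter (6.1.3.1).* If redacted text already says this, confirming it is enough. Report the number of OTH12PA2 subjects by arm, and run the analysis that excludes all of them as a sensitivity analysis only.

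The SAP already provides the route: "If updates to this table are needed, an amendment to the SAP needs to be implemented prior to DB lock". The cost is one sentence, one count by arm and one extra run of the primary model. No new data or patients are needed, and no clinical rule changes.

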## **6 Statistical methods for Pharmacodynamic (PD) parameters**

All subjects within the PD analysis set will be included in the PD data analysis.

### **6.1 Primary objective**

The primary aim of this study is to assess the induction of clinical remission by LYS006 compared to placebo in patients with mild to moderate UC using the total Mayo score.

#### **6.1.1 Variables**

The primary PD variable of this study is the clinical remission rate at the EoT visit CCI, i.e. the proportion of patients who reach the status of clinical remission at the EoT visit.

Clinical remission is based on total Mayo score, defined as a total Mayo score of 2 points or lower, with no individual subscore exceeding one point. The total Mayo score is the sum of four subscores, ranging from 0 to 12: stool frequency (recorded on a daily basis by a diary card), rectal bleeding (recorded on a daily basis by a diary card), endoscopic findings and Physician's

Global Assessment (PhGA). Each subscore grading ranges from 0 to 3, from free of disease to severe disease.

The stool frequency subscore should be calculated from the most recent three consecutive days within the week prior to the day of endoscopy bowel preparation. If three consecutive days are not available, the most recent non-consecutive 3 days within the week prior to the day of endoscopy bowel preparation should be used. The stool frequency subscore is the average of the 3 daily stool frequency subscores. The rectal bleeding subscore will be calculated in the same manner as stool frequency subscore.

Commercially Confidential Information

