8.3.1 Mayo Score

The Mayo score is an instrument designed to measure activity of UC. Mayo score comprises of four subscores: stool frequency, rectal bleeding, endoscopic findings and Physician's Global Assessment. Each subscore is graded from 0 to 3 with higher scores indicating more severe disease.

Table 8-2 Mayo score system for ulcerative colitis

Stoo	Stool frequency		
0	Normal number of bowel movements for this patient		
1	1 to 2 bowel movements more than normal		
2	3 to 4 bowel movements more than normal		
3	5 or more bowel movements more than normal		
Rect	al bleeding		
0	No blood seen		
1	Streaks of blood with stool less than half the time		
2	Obvious blood with stool most of the time		
3	Blood alone passes		
Ende	Endoscopic findings		
0	Normal or inactive disease		
1	Mild disease (erythema, decreased vascular pattern)		
2	Moderate disease (marked erythema, absent vascular pattern, any friability, erosions)		

3	Severe disease (spontaneous bleeding, ulceration)		
Phy	Physician's global assessment		
0	Normal		
1	Mild disease		
2	Moderate disease		
3	Severe disease		

The full Mayo score is the sum of four sub scores, ranging from 0 to 12.

Commercially Confidential Information

Clinical remission is defined in Section 12.4.1.

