8.3.1.1 Subject diary: Stool frequency and Rectal bleeding

Stool frequency and rectal bleeding are the main clinical symptoms of ulcerative colitis. Calculation of the Mayo score requires an assessment of stool frequency and rectal bleeding. Data on these clinical symptoms will be recorded by subjects on a daily basis using a paper diary until the end of the treatment period. Subjects will be provided with instructions on how to complete the paper diary at the screening visit. These should be reviewed at each visit until EoT by site staff, with retraining provided to subjects if the diaries are not completed correctly.

See the Site Operations Manual for guidance on training the subjects in the use of the diary and using the diary data to complete the Mayo score.

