12.8.1 Primary endpoint(s)

Figure 12-2 below illustrates the operating characteristics for the design of 45 subjects with 2:1 randomization ratio. The outcome of approximately 50% data is also shown in the same figure. The informative prior for the placebo group is included in the analysis. Assuming the true treatment difference in remission rate is 25% between LYS006 and placebo CCI

, the probability of meeting the dual efficacy criteria, stated in Section 12.4.2, is 86% with the full 45 subjects and 73%, for half the size. If there is no difference between LYS006 and placebo in clinical remission rate, the chance of meeting dual criteria is below 5% as shown in the left hand panel of the figure and the chance of meeting neither criterion is 92%, as shown in the right hand panel.

Figure 12-2 Operating charateristics for current design: 30 on LYS006 vs. 15 on placebo with historical placebo

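### Does averaging three daily diary scores, with no stated rounding step, leave the remission endpoint undefined?

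*SAP*

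**What the plan says.** SAP 6.1.1 takes three diary days from the week before bowel preparation, the most recent consecutive ones if available. It then states "The stool frequency subscore is the average of the 3 daily stool frequency subscores" and "The rectal bleeding subscore will be calculated in the same manner as stool frequency subscore". It describes the scale with "Each subscore grading ranges from 0 to 3, from free of disease to severe disease", and remission is "defined as a total Mayo score of 2 points or lower, with no individual subscore exceeding one point". A redacted block follows the averaging text directly.

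Protocol 8.3.1 states "Each subscore is graded from 0 to 3 with higher scores indicating more severe disease", and its Table 8-2 describes only the grades 0, 1, 2 and 3. Protocol 12.4.1 sets the same cut-offs: "Clinical remission is defined as a full Mayo score of 2 points or lower, with no individual subscore exceeding one point". For "using the diary data to complete the Mayo score", Protocol 8.3.1.1 refers sites to the Site Operations Manual, as does inclusion criterion 4 for completing the Mayo scores. That manual is not among the documents.

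**The concern.** The cut-offs were set on a whole-grade scale, but two of the four subscores become averages that can take values such as 1/3 or 4/3. Endoscopy 1, physician's global assessment (PhGA) 1, bleeding 0 and a stool average of 1/3 total 2.33, a failure; round the stool average to the nearest grade and the total is 2, a remission. Two programmers with different habits could therefore classify the same patient differently on the primary endpoint. With 30 and 15 patients and a threshold decision rule, one such patient could change the result. The documents also do not say whether the historical placebo data behind the prior, or the assumed 25-point effect, rest on whole grades or on averages.

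**Working it through.** **1. The plan's own figure.** Inputs from Protocol 12.4.2 and 12.8.1: 30 v 15 patients; LYS006 prior Beta(1/3, 1/3); placebo prior 0.43 Beta(18.9, 167.4) + 0.34 Beta(3.2, 24.2) + 0.03 Beta(1.0, 3.3) + 0.2 Beta(1, 1); success if P(diff > 0) > 0.90 and P(diff > 0.15) > 0.50. The planning placebo rate is redacted, so π is an assumption.

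With y remitters of 30 and x of 15, the LYS006 posterior is Beta(1/3 + y, 1/3 + 30 − y). The placebo posterior mixes Beta(a_k + x, b_k + 15 − x) with weights proportional to w_k B(a_k + x, b_k + 15 − x) / B(a_k, b_k). Then

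chance of success = Σ_y Σ_x Bin(y; 30, π + 0.25) · Bin(x; 15, π) · 1{both criteria met}.

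The protocol states that this chance "is 86% with the full 45 subjects and 73%, for half the size".

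| Placebo rate | 30 v 15, +25 points | 16 v 8, +25 points | No difference: both met | No difference: neither met |
|---|---|---|---|---|
| 11% (assumed) | 86.0% | 73.0% | 1.6% | 93.4% |
| 12% (assumed) | 86.6% | 73.6% | 2.3% | 91.5% |
| Protocol | 86% | 73% | below 5% | 92% |

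The split at half size is not stated. The table uses 16 v 8; splits of 14 v 7, 15 v 7 and 15 v 8 give 71.8% to 79.0% at these placebo rates. The planning figures are consistent with the stated rule. The scoring convention does not appear in the formula; it acts only through the remission rates put in.

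**2. Where the conventions differ.** Let a and b be the three-day sums for stool and bleeding (0 to 9 each), and e and p the endoscopy and PhGA grades (0 to 3). That gives 10 × 10 × 4 × 4 = 1,600 combinations.

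- *Plain average.* Remission needs a, b ≤ 3, e, p ≤ 1 and a + b + 3(e + p) ≤ 6. For e + p = 0 all 16 pairs (a, b) qualify; for e + p = 1 (two ways) 10 pairs each; for e + p = 2 only (0, 0). Total 16 + 20 + 1 = 37.
- *Nearest grade.* Sums 0–1 become 0 and sums 2–4 become 1. Grades (0, 0): 2 × 2 × 4 = 16. One grade 0 and the other 1: 2 × (2 × 3) × 3 = 36. Grades (1, 1): 3 × 3 × 1 = 9. Total 61.
- *Rounding up.* Sum 0 stays 0 and sums 1–3 become 1: 1 × 1 × 4 + 2 × (1 × 3) × 3 + 3 × 3 × 1 = 4 + 18 + 9 = 31.

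Against nearest rounding the plain average loses 61 − 37 = 24 and gains none: 7 because the total exceeds 2, 6 because a subscore exceeds 1, and 11 for both reasons. Against rounding up it gains 37 − 31 = 6 and loses none.

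**3. What the plain average rejects.** An average of 4/3 needs three grades that sum to 4, so at least one of the three days was graded 2 or worse. A total of 2.33 with endoscopy 1 and PhGA 1 means one further point on one of the three days. Declining to call these remission is a stricter reading of the cut-offs and a defensible one.

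**4. How far one patient matters.** Under the model of Protocol 12.4.2, the fewest LYS006 remitters that meet both criteria are 7, 8, 8, 9 and 11 for 0, 1, 2, 3 and 4 placebo remitters. With 1 or 2 on placebo, 8 of 30 succeeds and 7 does not. These count-only boundaries need not hold exactly under SAP 6.1.3, which adds baseline total Mayo score to the model.

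**5. Why power loss cannot be read from this.** Suppose, purely for illustration, that 12% and 37% are rates on rounded scores and that plain averaging removes 10% of remitters in each arm. The rates become 0.12 × 0.9 = 10.8% and 0.37 × 0.9 = 33.3%; the chance of success falls from 86.6% to 79.5%, and with no true difference from 2.3% to 1.5%. The 10% has no source in the documents. If the planning rates were on averages, the loss against the stated 86% is zero.

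**The case for a change.** The strongest case for acting is that the visible text does not say that thirds are meant to meet cut-offs written for whole grades. A confirming sentence would cost almost nothing, and settling the matter before unblinding would remove any room for choice on the primary endpoint. That the convention affects both arms alike is not a full answer: success depends on an absolute 15-point margin and on a placebo prior fixed from outside trials whose scoring is not described.

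The observation stands: no rounding step is visible, and the classification of some patients would differ. The inference of a defect does not. The SAP equates the subscore with the average and gives numeric cut-offs, so following the text yields one answer; rounding would be an added step. Table 8-2 describes grades for an assessment and does not say that a three-day summary must be whole. The redacted block and the manual are both natural homes for a rounding rule, and what redaction hides cannot be counted as absent. One patient deciding the result is a feature of any binary endpoint at this size. The 24 of 61 combinations are not a loss of patients either: among combinations with no bleeding on any of the three days the figure is 4 of 17, and neither fraction estimates a patient rate.

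**Conclusion.** No change to the plan follows. The visible rule is explicit and computable, identical in both arms, and gives a sound remission endpoint: stricter than nearest rounding (37 v 61 of 1,600 combinations) and slightly more lenient than rounding up (37 v 31). Choosing among them is a trade-off. Nearest rounding would admit more remitters in both arms and raise the chance of success both with and without a true effect, and no document supports it over the plain average. If the manual or the redacted text contains a rule, the analysts will apply it; if not, they apply the average as written.

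The patient-level effect is unknown, because the documents give no distribution of Mayo subscores at end of treatment. The 86% is not called into question: it reproduces at an assumed placebo rate of 11–12%. The conclusion rests on the SAP sentence being read as written and on the same convention being used for every patient. The study is described as a non-confirmatory proof of concept, which limits the weight that any one convention has to carry.
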